### 10.2.2 Total Duration of Platelet Response

The total duration of platelet response is defined in **Section 4.4** and will be analyzed in the similar way as duration of platelet response as mentioned in **Section 10.2.1**.

The same analyses as mentioned above will be conducted for the total duration of platelet response based on the additional definitions as mentioned in **Appendix 14.2**.

### 10.2.3 Reduction in the Dose of Concomitant ITP Therapy

This endpoint is defined in **Section 4.4**. The patient level listing of concomitant ITP use during the present study will be provided.

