4.3 Secondary Efficacy Endpoints

- The duration of any stable platelet response
- Proportion of subjects in whom a reduction in the dose of concomitant ITP therapy can be achieved while maintaining an adequate platelet count

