10.4.2 Secondary Efficacy Endpoints

The secondary efficacy endpoints are as follows:

- Duration of stable platelet response
- Proportion of subjects in whom a reduction in the dose of concomitant ITP therapy can be achieved while maintaining an adequate platelet count

Duration of stable platelet response is defined as the time, following active treatment, from when the subject first achieves a platelet count of at least 50,000/ μ L until the first of two visits with platelet counts < 50,000/ μ L that are at least 4 weeks apart without an intervening visit with a platelet count \geq 50,000/ μ L unrelated to rescue therapy. Subjects who drop out of the study before achieving a stable platelet response will be assigned a value of 0 for this endpoint. Subjects who drop out of or complete the study while still maintaining a stable platelet response will be censored as of the time of the last platelet measurement prior to dropping out or completing the study. For subjects who have achieved and are maintaining a stable platelet response but who discontinue treatment due to lack of efficacy or to an AE, duration of stable platelet response will be defined as the time from first achieving a platelet count of at least 50,000/ μ L until discontinuation of treatment. The duration of stable platelet response will be analyzed using the Kaplan-Meier method, and the Kaplan-Meier estimate of the median duration of stable platelet response will be presented together with the 95% CI for the true median.

Achieving a reduction in the dose of concomitant ITP therapy while maintaining an adequate platelet count will be summarized using counts and percentages and a 95% exact (Clopper-Pearson) CI for the true percentage. A two-sided, McNemar's test will be performed to compare the proportions of successes between the fostamatinib and placebo treatments.

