### 3.5. Changes to the Protocol-Specified Analyses

For the method of assigning subject to treatment (as mentioned in Section 3.2), protocol states that the responders will initiate open-label fostamatinib treatment with the dose and regimen that was efficacious in achieving a stable platelet response in Study C-935788-047 or C-935788-048. In reality, the patients were not required to be stable responders but rather to have at least one platelet count of at least 50,000/ $\mu$ L.

The protocol defines the baseline value as the last measurement for the corresponding variable prior to the first randomized dose at Visit 3 in Study C-935788-047 or C-935788-048. For the analyses described by this SAP, the baseline value will be defined as the last measurement for the corresponding variable prior to the first dose of fostamatinib in Study C-935788-047 or C-935788-048 (for fostamatinib patients in the previous study) or the present study (for placebo patients in the previous study), unless specified otherwise in the SAP.

For secondary efficacy endpoint, duration of stable platelet response, has been changed to duration of platelet response, the protocol specified that subjects who drop out of the study before achieving a platelet response will be assigned duration of platelet response of 0 and will be censored. In addition to the duration of platelet response, total duration of platelet response is also defined in **Section 4.4** in this SAP and will be analyzed.

For secondary efficacy endpoint, subjects with reduction in the dose of concomitant ITP therapy while maintaining an adequate platelet count (yes/no), the protocol states that a two-sided, McNemar's test was to be performed to compare the proportions of subjects achieving a reduction in the dose of concomitant ITP therapy while maintaining an adequate platelet count between the fostamatinib and placebo treatments. In this SAP, no McNemar's test will be performed, instead the patient level of listing for the concomitant ITP therapy using during the present study will be provided in data listing.

Also, per protocol version 5, one-sample t-test was to be used to evaluate the mean change from baseline for each post-baseline time point for the safety endpoints of systolic and diastolic blood

pressure, liver function test [i.e., ALT, AST, alkaline phosphatase, and bilirubin (total, direct, and indirect)] and ANC. This one-sample t-test will not be performed.

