#### 4.4. Secondary Efficacy Endpoints

The secondary efficacy endpoints are as follows:

- The duration of platelet response (months) and total duration of platelet response (months)
- Patients with reduction in the dose of concomitant ITP therapy while maintaining an adequate platelet count (yes/no)

Duration of platelet response will be defined as the length of time from when the patient first achieves a platelet count of at least 50,000/ $\mu$ L until the first of two visits with platelet counts < 50,000/ $\mu$ L that are at least 4 weeks apart without an intervening visit with a platelet count  $\geq$  50,000/ $\mu$ L unrelated to rescue therapy.

Four additional definitions of duration of platelet responses are stated in **Appendix 14.2**

Patients who drop out of the study before achieving a platelet response (i.e., achieving a platelet count of  $\geq$  50,000/ $\mu$ L) will be assigned a value of 0 for this endpoint. Patients who drop out of the study by the time of database lock while still maintaining a platelet response will be censored as of the time of the last platelet measurement prior to dropping out of the study. Similarly, patients who remain in the study by the time of database lock while still maintaining a platelet response will be censored as of the time of the last platelet measurement prior to the time of database lock. For patients who have achieved and are maintaining a platelet response but who have discontinued treatment due to lack of efficacy or to an AE by the time of database lock, duration of platelet response will be defined as the time from first achieving a platelet count of  $\geq$  50,000/ $\mu$ L until discontinuation of treatment.

The total duration of platelet response is defined as the sum of all durations of platelet responses.

Regarding the secondary efficacy endpoint of patients with reduction in the dose of concomitant ITP therapy while maintaining an adequate platelet (yes/no), a patient is said to have reduction while maintaining an adequate platelet count if the date of reduction of dose of concomitant ITP therapy occurs within the span of the duration of a platelet response during the C-935788-049 study and the reduction was not prompted by AE.

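### SAP 10.2.3 replaces the protocol's percentage and exact confidence interval for reduction of concomitant ITP therapy with a medication listing, and SAP 3.5 declares only the loss of McNemar's test

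*SAP*

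**What the plan says.** Protocol 4.3 names the endpoint as a proportion: "Proportion of subjects in whom a reduction in the dose of concomitant ITP therapy can be achieved while maintaining an adequate platelet count". Protocol 10.4.2, and the synopsis with it, says that this "will be summarized using counts and percentages and a 95% exact (Clopper-Pearson) CI for the true percentage". It adds that a two-sided "McNemar's test will be performed to compare the proportions of successes between the fostamatinib and placebo treatments".

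SAP 4.4 retains the endpoint as a per-patient yes/no variable and gives a success rule: "a patient is said to have reduction while maintaining an adequate platelet count if the date of reduction of dose of concomitant ITP therapy" falls inside a platelet response during study 049, and an adverse event did not prompt the reduction.

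SAP 10.2.3 refers back to that definition, and its only planned output is: "The patient level listing of concomitant ITP use during the present study will be provided".

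SAP 3.5 records the change. It restates the protocol plan as a McNemar comparison, says that the test will not be done, and offers "instead the patient level of listing for the concomitant ITP therapy". It does not mention the count, percentage or CI, and gives no reason.

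Protocol 10.2 and SAP 6.1 both place all efficacy analyses on the Treated Population.

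**The concern.** The SAP defines a binary endpoint and then plans nothing that uses the definition. A listing of medication use shows which ITP drugs a patient took. It does not show whether the patient met the success rule. To find that out, a reader would have to match each dose-reduction date to the patient's response periods and to the reason for the reduction.

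Dropping McNemar's test does not explain the rest. The percentage and its CI are a one-group description of patients on fostamatinib in 049 and need no placebo comparison.

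At stake is whether a prespecified secondary endpoint has a planned result. Any percentage reported later would have to be counted from a listing, outside the SAP's planned outputs.

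**Working it through.** **Step 1. Planned items side by side.**

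| Item for this endpoint | Protocol 10.4.2 | SAP 10.2.3 | Declared as dropped in SAP 3.5? |
|---|---|---|---|
| Count and percentage | Yes | No | No |
| Exact Clopper-Pearson 95% CI | Yes | No | No |
| Two-sided McNemar's test | Yes | No | Yes |
| Patient-level listing | No | Yes | Announced as the replacement |

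None of the three protocol items survives, and one of the three omissions is declared.

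**Step 2. Does another SAP section supply the estimate?**

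- SAP 11.7 tabulates ITP medications by ATC class and preferred term. That is use, not reduction during a response.
- SAP 5.1 has a general line that categorical variables get frequencies and percentages. It does not name this endpoint and provides no CI.
- SAP 10.3 states explicitly that each exploratory efficacy endpoint gets the frequency and percentage of patients achieving it. The SAP says so where it wants a percentage, and SAP 10.2.3 does not.
- SAP 3.5 also drops the one-sample t-tests on blood pressure, liver tests and ANC, but SAP 11.2 and 11.3 keep the descriptive summaries of laboratory tests and vital signs. Here the descriptive summary goes with the test.

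**Step 3. Size.** The documents give no rate, no power calculation and no number of patients on concomitant ITP therapy, so there is no planned figure to reproduce. The one documented number is the enrolment cap of 150 (Protocol 5.1, SAP 3.1). The rest is assumed.

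For x successes in n patients, the exact 95% limits are the 0.025 quantile of Beta(x, n − x + 1) and the 0.975 quantile of Beta(x + 1, n − x).

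Assume 12 successes, 60 patients on therapy and 150 treated:

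- Treated Population: 12/150 = 8.0%, CI 4.2% to 13.6%.
- On-therapy patients: 12/60 = 20.0%, CI 10.8% to 32.3%.
- Ratio of the two estimates: 20.0/8.0 = 150/60 = 2.5.

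Holding the assumed on-therapy success rate at 20% and varying the number on therapy:

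| On therapy (assumed) | On-therapy estimate (95% CI) | Same successes over 150 treated (95% CI) |
|---|---|---|
| 30 | 6/30 = 20.0% (7.7% to 38.6%) | 6/150 = 4.0% (1.5% to 8.5%) |
| 50 | 10/50 = 20.0% (10.0% to 33.7%) | 10/150 = 6.7% (3.2% to 11.9%) |
| 75 | 15/75 = 20.0% (11.6% to 30.8%) | 15/150 = 10.0% (5.7% to 16.0%) |
| 150 | 30/150 = 20.0% (13.9% to 27.3%) | same |

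The intervals are wide enough that a percentage without its CI would mislead. The two denominators also answer different questions.

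**The case against.** **The change is disclosed.** SAP 3.5 is the section for changes, and it announces the listing. That stands, so a reader should not infer that the move to a listing was concealed. What SAP 3.5 does not say is that the protocol also planned a percentage and CI and that these go too.

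**SAP 5.1 may still cover a percentage.** The endpoint is yes/no, and categorical variables are to be summarized by frequencies and percentages. This is arguable, but the specific text of SAP 10.2.3 and the replacement wording in SAP 3.5 point to a listing only, and SAP 5.1 gives no CI on any reading. Protocol 10.4.2 still specifies both. The supportable statement is therefore that the SAP does not carry the estimate forward. It would go too far to say that the trial can produce none.

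**The denominator is not open.** A reader might infer that any later percentage would rest on a denominator picked after the data are seen, or that the planned row would be the 20% in the illustration. The documents support neither. Protocol 10.2 and SAP 6.1 fix the Treated Population, so under the assumed inputs the planned row is 8.0%. The fair criticism is that this denominator includes patients who have no concomitant therapy to reduce. An on-therapy denominator would be a new proposal and not a restoration.

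**The endpoint carries limited weight.** The primary objective is safety, the study is open-label without a sample-size calculation, and Protocol 7.7.1 leaves tapering to discretion, so the proportion partly reflects investigator choice. All of that stands. It limits how the estimate is interpreted, but does not explain omitting it.

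**Conclusion.** The point holds as a mismatch between protocol and SAP. SAP 10.2.3 omits the count, percentage and exact CI that Protocol 10.4.2 specifies, although SAP 4.4 keeps a usable definition, and SAP 3.5 declares only the loss of the test. Followed as written, the SAP leaves one of the protocol's two secondary efficacy endpoints without an estimate. No primary or safety conclusion depends on it, so this should be corrected but does not threaten the study.

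The textual finding rests on no assumption. The numerical illustration does: the success counts and the numbers on therapy are assumed, and only the maximum of 150 is documented.

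**What to change.** 1. In SAP 10.2.3, restore the count, percentage and Clopper-Pearson 95% CI, applying the SAP 4.4 definition to the Treated Population.
2. Add the same summary among patients receiving concomitant ITP therapy at their first 049 dose, because patients without such therapy have nothing to reduce. Protocol 7.7.1 bars adding new ITP treatments, so this group is close to the set of patients in whom a reduction is possible. Declare it in SAP 3.5 as a new analysis.
3. In SAP 3.5, state that McNemar's test is the only protocol item removed for this endpoint. The test can stay dropped.
4. Keep the listing and add each patient's endpoint status to it.

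The cost is small, but the flag is not yet available: it is defined in SAP 4.4 and no output currently derives it. One flag and one or two summary rows are needed. Confirm first that the eCRF captures the date of and reason for each dose reduction, since Protocol 7.7 says only that concomitant therapies are recorded at all visits.

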## 10.3 Additional Efficacy Analyses

Platelet count will be summarized by scheduled visit using descriptive statistics. Platelet count will also be summarized by

- Study C-935788-047/C-935788-048 primary efficacy endpoint responder status,

- Study C-935788-047/C-935788-048 primary efficacy endpoint responder status and C-935788-049 primary efficacy version 2 responder status. This is for C-935788-047/C-935788-048 placebo patients entering C-935788-049 study
- For study C-935788-049 primary efficacy endpoint version 1 responders. This is for all C-935788-047/C-935788-048 patients entering C-935788-049 study

The summaries above will be performed by prior study treatment group in C-935788-047/ C-935788-048 studies and overall.

For each of exploratory efficacy endpoints mentioned in **Appendix 14.1**, frequencies and percentages of patients achieving the endpoint (Yes) will be provided.

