7.3 Discontinuation of Nonresponders

After 3 months (12 weeks) of treatment, (and a minimum of 4 weeks treatment at 150 mg PO *bid*, unless this higher dose was not tolerated), any subject whose platelet count consistently

remains $< 50,000/\mu\text{L}$ should be discontinued from the study, unless tangible clinical benefit from the use of fostamatinib is evident and the Sponsor agrees (discuss any exceptions with the Sponsor's Medical Monitor). Examples of tangible clinical benefit may include, but are not limited to:

- Credible increase in platelet count (eg, increase in platelet count of at least $20,000/\mu\text{L}$ over the initial baseline to a count $\geq 30,000/\mu\text{L}$)
- Reduction in bleeding
- Reduction in the need for rescue therapy

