7.9 Withdrawal from Study

Subjects will be discontinued from study treatment in the following situations:

- Subject decision. A subject is free to withdraw consent and discontinue participation in the study at any time.
- AE based on Investigator judgment
- Subject is uncooperative or noncompliant and will not/cannot adhere to study responsibilities, including failure to complete patient diary or appear for study visits
- Subject was erroneously enrolled in the study
- Pregnancy in a female participant
- Subject lost to follow-up despite the diligent efforts of site personnel to trace subject

Subjects may be withdrawn from study treatment and from the study in the event of lack of platelet response (defined as platelet count $< 50,000/\mu\text{L}$) following 3 months (12 weeks) of treatment unless Sponsor approval is obtained.

Subjects who are withdrawn from the study during the treatment period will have a withdrawal visit equivalent to the Follow-up Visit assessments. The reason for withdrawal must be noted on the eCRF. If an SAE is present at the withdrawal visit or at the subject's last participation in the study, the SAE should be followed as described in [Section 9.2](#).

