### **5.3 Handling of Dropouts and Missing Data**

No imputation will be performed for missing data

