## **6.0 ANALYSIS POPULATIONS**

### **6.1. Treated Population**

The Treated Population will include all enrolled and treated patients in the present study. All efficacy and safety analyses will be performed on the Treated Population.

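### By-visit platelet summaries use observed cases while the protocol takes patients off study for low counts, so later visits are biased upward if low-count patients leave faster than responders

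*SAP*

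**What the plan says.** SAP 10.3, headed "Additional Efficacy Analyses", plans this: "Platelet count will be summarized by scheduled visit using descriptive statistics". The summary is repeated by prior-study responder status, by Version 2 status in former placebo patients, and within a further subset: "For study C-935788-049 primary efficacy endpoint version 1 responders". It is shown by prior treatment group and overall.

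Three other provisions decide who contributes at each visit.

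- SAP 5.3: "No imputation will be performed for missing data". Protocol 10.8 says the same. SAP 6.1 adds "All efficacy and safety analyses will be performed on the Treated Population", but no fixed cohort is defined for the by-visit table.
- Protocol 7.3, matched by 5.3: after 12 weeks, with at least 4 of them at the higher dose if tolerated, a patient whose count consistently remains below 50,000/µL "should be discontinued from the study, unless tangible clinical benefit from the use of fostamatinib is evident and the Sponsor agrees". Protocol 7.9 words it more softly: "Subjects may be withdrawn from study treatment and from the study in the event of lack of platelet response". The two wordings need to be reconciled.
- SAP 5.1 excludes counts taken within 28 days of rescue from every platelet analysis. Protocol 7.4 permits rescue only at counts below 50,000/µL.

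Visits run to Month 60.

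**The concern.** Both ways of leaving the table, discontinuation and the post-rescue exclusion, are triggered by a low value of the quantity being tabulated. Up to about Month 3 the table describes nearly everyone. After that it describes patients who were kept largely because their counts were adequate. The mean and median can then rise although no patient has changed, and a real decline among responders can be hidden.

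The efficacy objective in SAP 2.0 concerns both achieving and maintaining a stable count. A reader following the by-visit table could take a change in who is measured for a strengthening or persistence of response. The text of SAP 10.3 does not label the table as observed cases, and it does not ask for the baseline of the patients remaining at each visit.

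**Working it through.** The documents give no expected by-visit values, sample size calculation or power figure, so there is no planned number to reproduce. The check is illustrative: hold every patient's count distribution constant, let patients leave, and see what the table shows.

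**Inputs**

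- Share sustained: 8 of 18, from the pilot trial in Protocol 3.3. The pilot defined sustained as increased counts on at least 67% of occasions, not as at least 50,000/µL, so this is a stand-in.
- Typical counts (assumed): log-normal with medians 80,000 and 18,000/µL and log SD 0.45.
- Share of non-sustained patients kept (assumed): 20% or 40%. In the pilot, 4 transient responders stayed on drug for clinical improvement. That is 4 of the 10 non-sustained patients, or 40%, so the second value is closer to the pilot.

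**Formulas**

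- Group mean = median × exp(0.45²/2) = median × 1.1066. This gives 88.5 and 19.9 (×1,000/µL).
- Probability of at least 50,000/µL: Φ(ln(80/50)/0.45) = 0.852 for sustained patients and Φ(ln(18/50)/0.45) = 0.012 for the others.
- With a sustained and b non-sustained patients remaining out of 18, observed mean = (88.5a + 19.9b)/(a + b). Observed percent = (0.852a + 0.012b)/(a + b). All-Treated percent = (0.852a + 0.012b)/18.

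**Results** (means and medians in ×1,000/µL)

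| Scenario | a, b | Observed mean | Observed median | Observed ≥50,000 | All Treated ≥50,000 |
|---|---|---|---|---|---|
| Everyone present | 8, 10 | 50.4 | 31 | 38.5% | 38.5% |
| 20% of others kept | 8, 2 | 74.8 | 69 | 68% | 38% |
| 40% of others kept | 8, 4 | 65.7 | 59 | 57% | 38% |
| 40% kept, 20% of responders lost | 6.4, 4 | 62.1 | 54 | 53% | 31% |
| Half of each group lost | 4, 5 | 50.4 | 31 | 38.5% | 19% |

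In the second and third rows nothing has happened to any patient. In the fourth, fewer patients benefit, yet the observed figures are higher than at the start.

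**Check with other counts.** Take the pilot responders' median baseline and peak, 16 and 105 (×1,000/µL), as the typical low and high counts in 150 patients, 83 of them low. The starting mean is (83×16 + 67×105)/150 = 55.8. If about half of the low group leaves, it becomes (42×16 + 67×105)/109 = 70.7. If about a quarter leaves, it becomes (62×16 + 67×105)/129 = 62.2. If all of them leave while responders truly fall by 20% to 84, the table shows 84, although the all-patient mean has dropped to 16×10/18 + 84×8/18 = 46.2.

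**Where the effect is small.** In a simulation with these typical counts, 80% low-count patients and only a quarter of them leaving, the median moved only from about 19 to 20.

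**The case against.** The strongest reply is that little rests on this table. It is additional and descriptive, and it tests nothing. The primary objective is safety. Version 1 applies to all patients entering the study: never-responders fail its first criterion, and stopping for lack of efficacy or an AE within 12 months of response counts as failure (SAP 4.3, 10.1.1). Discontinuation is also not automatic, because agreed clinical benefit exempts a patient and Protocol 7.9 is permissive. Responders leave too, and SAP 7.0 reports reasons for discontinuation. All of this stands, and it limits how much the point matters.

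Several stronger readings are tempting, and the documents do not support them.

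- *This is the trial's long-term efficacy curve.* The documents never call it that.
- *The bias always favours fostamatinib, or the curve must rise.* The shift needs faster loss of low-count patients; equal loss gives none. The arithmetic shows one step after about Month 3, not a steady deepening to Month 60.
- *No all-Treated percentage is planned.* SAP 10.3 also reports frequencies for the Appendix 14.1 endpoints, which are redacted. They cannot be judged.
- *The Kaplan-Meier duration counts these stops as failures and so will contradict the table.* SAP 4.4 assigns 0 to patients who drop out before responding, and SAP 3.5 describes them as censored. Their treatment as events is not established.

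The planned subgroups do not remove the problem. Version 1 responders largely escape the early loss of nonresponders, but they are selected on the counts being displayed and face the same attrition after their 12-month window. The other strata still use observed cases. The 28-day exclusion properly avoids crediting the drug with a rescue effect, but it drops the patient from the visit and does not count the visit as below threshold.

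**Conclusion.** The point holds as a statement about mechanism and direction. Missingness depends on platelet count, nothing is imputed, and the observed by-visit mean and median, with any percentage computed on the same patients, are biased upward when low-count patients leave faster than responders, which is what Protocol 7.3 makes likely.

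The size is not known from the documents. Under the stated assumptions a constant mean of 50,000/µL would appear as about 62,000 to 75,000/µL, with 66,000 for the retention closest to the pilot. The result depends on the share of low-count patients, the fraction who leave, the assumed counts and the loss of responders. The main efficacy conclusions do not rest on this table, so this is an inexpensive improvement to the plan and not a flaw in its primary analysis.

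**What to change.** In SAP 10.3, alongside the observed-count table, add the number and percent of all Treated patients with a platelet count of at least 50,000/µL at each scheduled visit, by prior treatment group and overall.

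- Count patients who discontinued for lack of efficacy or an AE, and those inside the 28-day post-rescue window, as not meeting the threshold.
- State the rule for other withdrawals (consent, loss to follow-up, pregnancy). For example, count them as not meeting it too, with a sensitivity analysis.
- Remove patients from the denominator only for visits they could not reach because of database lock or commercial availability.
- Declare this an explicit exception to SAP 5.3 (no imputation) and SAP 5.1 (post-rescue exclusion).

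Label the existing table as observed cases, show n and the same patients' baseline count at each visit, and note that the Version 1 responder curve is selected on outcome. Reconcile the wording of Protocol 7.3 and 7.9.

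The cost is SAP wording and one extra table from data already collected. Trial conduct does not change. The long-term percentages will look less favourable.
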